
1. Once the patient has been enrolled and eligibility has been established, the order of the treatment visits will be randomized in blocks of 2 patients.
 
2. In Part 1, each patient will participate in 2 treatment visits: 1 with the iPhone-based BP using ZP4207 and 1 with the iPhone-based BP using Lilly glucagon in a randomized order. In Part 2, each patient will participate in 2 treatment visits: 1 with the iLet using ZP4207 and 1 with the iLet using Lilly glucagon in a randomized order. Up to 2 patients may participate in the trial per day.
 
3. The night before the visit, patients will place a Dexcom G4 CGM sensor in the abdominal skin and calibrate the sensor when prompted using the provided Nova StatStrip Xpress meter. Patients will be asked to arrive at the visit at least 1 hour in advance of the start of the BP having fasted since 12:00 AM the night before (treatment with simple carbohydrate of up to 30 g for a low is allowed). If the patient is not fasted, the visit will be rescheduled within the visit window. If BG is >250 mg/dL, the visit will be rescheduled within the visit window. If BG is <50 mg/dL, treatment with simple carbohydrate is allowed. If the patient experiences persistent hypoglycemia, the visit will be rescheduled within the visit window.
 
4. Visit 3 will take place at least 48 hours after screening (Visit 1) and no more than 30 days after screening (Visit 1).
 
5. There will be a 24-hour minimum washout between Visit 3 and Visit 4 and a maximum of 3 weeks between Visit 3 and Visit 4.
 
6. Visit 5 will take place 10 days ±3 days from Visit 4.
 
7. Visit 6 will take place 25 days ±4 days from Visit 4.
 
8. Height and physical examination will be measured at Visit 1 only.
 
9. Vital signs including body temperature and blood pressure will be obtained at visit start and visit end.
 
10. At visit start and visit end.
 
11. Urine HCG pregnancy test only for women of childbearing potential. The date of the last menstrual period in female patients will be obtained at Visit 1 only.
 
12. Test for FSH level only for postmenopausal women amenorrheic for less than 1 year.
 
13. If indicated by history.
 
14. Patients will be trained in the insertion and calibration of the Dexcom G4 sensor, diabetes management (e.g., basal insulin rate adjustment by insulin pump) during fasting prior to and between the treatment visits, and trial policies and procedures.
 
15. Collected at least hourly. If BG is <150 mg/dL, then sampling will be every 30 minutes. If BG is <100 mg/dL, then sampling will be every 20 minutes. If BG is <80 mg/dL, then sampling will be every 10 minutes.
 
16. Collected at least hourly. If BG is <150 mg/dL, more frequent samples for plasma ZP4207/glucagon may be drawn at the discretion of the Investigator.
 
17. Once the infusion sites have been placed but no drug has yet been administered.
 
18. Between approximately Hour 3 and Hour 4.
 
19. Between approximately Hour 6 and Hour 7.
 
20. Before the start of dosing.
 
ADA = anti-drug antibodies; BG = blood glucose; BP = bionic pancreas; CGM = continuous glucose monitor; ECG = electrocardiogram; FSH = follicle-stimulating hormone; HbA1c = hemoglobin A1c; HCG = human chorionic gonadotropin; VAS = visual analog scale.
						

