4.6 Primary Endpoint Analyses

All safety analyses will be performed using the Safety Analysis Set. Safety variables will be summarized using descriptive statistics for continuous variables and frequency and percentage for categorical variables. These safety analyses will be compared qualitatively between the two treatment groups.

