4.6.1 Adverse Events

All AEs from the time of signing the informed consent through trial completion will be recorded on the electronic Case Report Form (eCRF). An AE is any untoward medical occurrence in a clinical trial patient administered an IMP and which does not necessarily have a causal relationship with the treatment. An AE can, therefore, be any unfavorable and unintended sign (e.g., and abnormal laboratory finding), symptom, or disease temporarily associated with the use of an IMP, whether or not considered related to the IMP. For this trial, insulin (insulin lispro, Lilly Humalog), glucagon (glucagon for inject, Eli Lilly), and ZP4207 are all regarded as IMP.

Adverse events will be coded using the latest version of the Medical Dictionary for Regulatory Activities (MedDRA). The actual used version number will be documented in the database. Individual AEs will be presented in a listing including relationship to trial product/device, severity, and treatment period at onset. If more than 20 treatment-emergent AEs (AEs with onset after [first] dosing at Visit 3 until the follow-up Visit 6) are registered, a summary table including number of AEs, number of patients with at least 1 AE, and percentage of exposed patients with at least 1 AE will be made by system organ class and treatment period at onset. Specific by-patient listings of serious adverse events (SAEs) and treatment-emergent AEs leading to discontinuation will be provided.

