4.6.2 Clinical Laboratory Tests

Summary statistics of clinical chemistry and hematology parameters will be provided by treatment sequence at each time point (i.e. start of visit and end of visit) within each period. Change from the start of the visit will also be summarized by treatment. Frequency counts and percentages of patients with normal and abnormal results, for parameters of interest, will also be presented by treatment sequence. Listings of patients with abnormal results will be provided.

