4.7.1 Bionic Pancreas Function Endpoints

The plasma ZP4207/Lilly glucagon concentration will be summarized descriptively at each time point by treatment group (e.g. n, mean, SD, coefficient of variation [CV%], median, minimum, and maximum). Mean concentration will be plotted over time, by treatment group. Individual plasma concentration-time curves will be plotted by patient.

The analysis of BP function endpoints will be on an intention-to-treat basis. In cases where a treatment arm was not completed (and that arm was not repeated according to protocol criteria), available data from that arm will be used in the data analysis.

A paired t-test or the Wilcoxon signed rank test for comparison of means with normally or non-normally distributed residuals, respectively, will be used. The Shapiro-Wilk test will be used to determine the normality of the residuals for each comparison. The residuals will be obtained from an ANOVA model with treatment group as the fixed effect. If the p-value of the test is less than 0.001, the non-parametric method will be utilized to analyze the endpoint parameter. The sample SAS code for the paired t-test analysis involving the average percent of insulin dose amounts successfully delivered by the pump is included here:

```
.....  
Note: InsTrt1 = the average percent of insulin dose amount successfully  
delivered by the pump during treatment with Lilly glucagon.  
InsTrt2 = the average percent of insulin dose amount successfully  
delivered by the pump during treatment with ZP4207.  
.....  
proc ttest ;  
paired InsTrt1*InsTrt2;  
run;
```

In a secondary analysis, any period effect and any interaction between treatment and period will be looked for, although no such interaction is predicted for the efficacy outcomes. The efficacy outcomes will be analyzed using a mixed model including terms for treatment and period as fixed effects, an interaction term, and subject nested within sequence as a random effect. A patient must have a data value for both periods in order to be included in the analysis for the given parameter. The sample SAS code for this analysis is included here:

```
.....  
Note: Insulin = the average percent of insulin dose amounts successfully  
delivered by the pump  
subject = subject identification number.  
sequence = sequence order (1=glucagon/ZP4207, 2=ZP4207/glucagon).  
treatment = treatment group (1=Lilly glucagon, 2=ZP4207).  
period = analysis period number (1=Visit 3, 2=Visit 4).  
.....
```

```

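### Two primary safety displays, the AE summary table and the normal/abnormal lab counts, are laid out by period or sequence and so do not show the ZP4207-versus-glucagon comparison that SAP 4.6 promises

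*SAP*

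**What the plan says.** Number and type of AEs is the first-listed component of the primary endpoint (SAP 3.2.1), and clinical laboratory measurements are the second. For the whole of the safety analysis, section 4.6 states: "These safety analyses will be compared qualitatively between the two treatment groups".

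Section 4.6.1 then provides for:

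- an AE listing: "Individual AEs will be presented in a listing including relationship to trial product/device, severity, and treatment period at onset";
- one AE summary table, subject to a condition: "If more than 20 treatment-emergent AEs (AEs with onset after [first] dosing at Visit 3 until the follow-up Visit 6) are registered";
- a layout for that table in which the number of AEs, the number of patients affected and the "percentage of exposed patients with at least 1 AE will be made by system organ class and treatment period at onset".

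Section 4.6.2 gives lab summary statistics by sequence at each time point within each period. It adds: "Change from the start of the visit will also be summarized by treatment". The counts of normal and abnormal results, "for parameters of interest, will also be presented by treatment sequence".

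Period is defined only in the code notes of section 4.7.1: "period = analysis period number (1=Visit 3, 2=Visit 4". The same notes define sequence as the order of the two drugs. Section 3.1 randomises that order in blocks of 2, and section 4.1 keeps the analyses of Parts 1 and 2 apart.

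**The concern.** A table answers a between-drug question only if drug is one of its columns or can be worked out from them. The AE table has columns for period, and the abnormal-lab counts have columns for sequence. In this design each of those margins averages over both drugs. A real difference in AE frequency between ZP4207 and Lilly glucagon would cancel out of the one AE table the plan provides, and a table showing no difference would be uninformative about safety.

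The event-count condition adds to this. With 20 or fewer treatment-emergent AEs there is no AE table at all, only a listing whose stated contents include period but not the drug in use at onset.

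**Working it through.** The SAP has no figure to reproduce here; section 5 says no formal sample size calculation was made. Two checks apply.

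**1. Can the drug difference be recovered from period totals or sequence totals?**

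The crossover has four cells, taken from the section 4.7.1 code notes:

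| | Period 1 (Visit 3) | Period 2 (Visit 4) |
|---|---|---|
| Sequence 1 | glucagon | ZP4207 |
| Sequence 2 | ZP4207 | glucagon |

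Let *z* and *g* be the proportions of patients with an AE on ZP4207 and on glucagon, with *n1* and *n2* patients per sequence and no period effect.

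- Period 1 column: (*n1*·*g* + *n2*·*z*)/(*n1* + *n2*)
- Period 2 column: (*n1*·*z* + *n2*·*g*)/(*n1* + *n2*)
- Period 2 minus period 1: (*n1* − *n2*)(*z* − *g*)/(*n1* + *n2*), which is 0 when *n1* = *n2*
- Patient-periods in either sequence: (*g* + *z*)/2

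Take 5 patients per sequence (up to 10 are expected to complete each part), with illustrative rates *z* = 0.60 and *g* = 0.20:

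- Period 1: (5 × 0.20 + 5 × 0.60)/10 = 0.40
- Period 2: (5 × 0.60 + 5 × 0.20)/10 = 0.40
- Each sequence: (0.20 + 0.60)/2 = 0.40

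Very different drug results give identical margins:

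| ZP4207 | Glucagon | Period 1 | Period 2 | Sequence 1 (patient-periods) | Sequence 2 (patient-periods) |
|---|---|---|---|---|---|
| 6/10 | 2/10 | 4/10 | 4/10 | 4/10 | 4/10 |
| 2/10 | 6/10 | 4/10 | 4/10 | 4/10 | 4/10 |
| 4/10 | 4/10 | 4/10 | 4/10 | 4/10 | 4/10 |
| 8/10 | 0/10 | 4/10 | 4/10 | 4/10 | 4/10 |

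The general statement, with cells ordered S1P1, S1P2, S2P1, S2P2, uses these contrasts: drug (−1, 1, 1, −1), period (−1, 1, −1, 1) and sequence (−1, −1, 1, 1).

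- Drug · period = 1 + 1 − 1 − 1 = 0
- Drug · sequence = 1 − 1 + 1 − 1 = 0

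The period and sequence totals together have rank 3, and adding the drug contrast raises it to 4. The drug comparison is therefore outside what those totals can show. It can be read only from a split by treatment or from the sequence-by-period cells.

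A small imbalance does not rescue the table. With 5 and 4 patients, the 40-point drug difference appears as (5 − 4)/9 × 40 = 4.4 points between periods, and it cannot be told apart from a period effect.

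**2. How likely is it that no AE table is made?**

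More than 20 events means a mean above 20/10 = 2.0 per patient if counted within a part of 10, or above 20/20 = 1.0 if counted over 20 patients. The SAP does not say which applies and gives no AE rate. Taking Poisson counts with an assumed mean per patient, the chance of 20 or fewer events is:

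| Patients counted | 0.5 per patient | 1 | 1.5 | 2 | 3 |
|---|---|---|---|---|---|
| 10 (one part) | above 99% | 99.8% | 91.7% | 55.9% | 3.5% |
| 12 (one part) | above 99% | 98.8% | 73.1% | 24.3% | 0.3% |
| 20 (both parts) | 99.8% | 55.9% | 3.5% | about 0 | about 0 |
| 24 (both parts) | 98.8% | 24.3% | 0.3% | about 0 | about 0 |

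The 20 and 24 are the range of randomised patients in section 5; 12 is half of 24. If the condition is applied per part, as many as 20 + 20 = 40 AEs across the trial could go untabulated. That figure depends on the per-part reading.

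**The case against.** **The wording may mean drug.** Period is defined in a code note for a secondary mixed model, not for AEs. Section 4.6.1 speaks of treatment period and of exposed patients, and sections 4.1 and 4.6 both say the arms are compared. Periods labelled by drug are a possible intention. But the SAP's only definition of period is by visit, and elsewhere in the safety section it writes treatment or treatment group when it means drug. As written, the text does not fix a by-drug table.

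**The lab sentence may inherit its layout.** It follows a description by sequence within period, which does identify the drug. The sentence itself names sequence alone, so this too needs stating.

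**Table shells sit in separate specifications.** They may show drug as a column. They are not at hand, and section 1 lets minor deviations from the tables go unreported in the study report, so they do not cure the SAP text.

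**A short listing is readable.** With 20 or fewer events in small parts and only a qualitative comparison planned, this is fair. The listing should then name the drug at onset, and its described contents do not.

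**Stronger inferences a reader might draw.**

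- That the primary safety comparison as a whole cannot be read. The SAP does not support this. Changes in labs, vital signs and ECG, and local tolerability, pain and nausea VAS scores, are summarised by treatment (4.6.2, 4.6.4, 4.6.5, 4.6.7, 4.6.8). Lab, vital-sign and ECG summary statistics are by sequence within period. A difference in nausea scores, for instance, would be visible by drug.
- That unequal follow-up biases the comparison. Visit 4 follows Visit 3 by 24 hours to 3 weeks, while "Visit 6 will take place 25 days ±4 days from Visit 4", that is 21 to 29 days. But the SAP sets no AE window per period, and randomised order places each drug in each window about equally.
- That Visit 6 labs enter no summary. The restriction to visit start and end is attached to the summary statistics; the normal/abnormal sentence carries no visit restriction.

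**Conclusion.** The point holds for two displays, the AE summary table and the normal/abnormal lab counts. As written, neither shows the between-drug comparison promised in section 4.6, and in a balanced crossover their margins carry no information on it: a 40-point difference shows as 0. This rests on reading period as the SAP defines it, on near-equal sequence sizes from blocks of 2, and on the lab counts being by sequence alone.

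The AE table may also not exist. At an assumed 1 AE per patient, the chance of that is 99.8% if the condition is applied to a part of 10 patients and 55.9% if applied to 20 patients in total.

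No data are lost, because the patient listings and the randomisation order allow the drug at onset to be reconstructed by hand. No test, estimate or data collection is affected. A prespecified display of the first-listed primary endpoint component should not depend on that reconstruction. This should be fixed, but it does not undermine the safety analysis as a whole.

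**What to change.** In section 4.6.1, within each part:

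- Tabulate treatment-emergent AEs by treatment received at onset, defined as the last glucagon product given (insulin is an IMP in every arm and cannot serve for this). Do so regardless of the number of events, and delete the condition of more than 20.
- Use the patients dosed with that product as the denominator.
- Show AEs with onset during a treatment visit separately from those in washout or follow-up. After Visit 4 a completer has received both products, so attribution to the last one is only a convention.
- Add treatment at onset to the AE listing.

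In section 4.6.2, present normal/abnormal counts by treatment, or state that they are by sequence within period.

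The cost is SAP wording and a few table columns. Trial conduct, data collection and sample size do not change, and period or sequence tables can stay as supportive output.

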4.6.2 Clinical Laboratory Tests

Summary statistics of clinical chemistry and hematology parameters will be provided by treatment sequence at each time point (i.e. start of visit and end of visit) within each period. Change from the start of the visit will also be summarized by treatment. Frequency counts and percentages of patients with normal and abnormal results, for parameters of interest, will also be presented by treatment sequence. Listings of patients with abnormal results will be provided.

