Screening labs – HbA1c, optional fractionated metanephrines [13]	X					
Safety lab sampling including chemistry and hematology	X		X [10]	X [10]		X
Training on devices [14]		X				
Monitored BP use			X	X		
Plasma glucose sampling [15]			X	X		
ZP4207/glucagon exposure sampling [16]			X	X		
Nausea and infusion site pain VAS and infusion site reaction Draize scale (visit start [17], hourly, & visit end)			X	X		

Trial Visit	Visit 1 [1] Screening	Visit 2 Training	Visit 3 [2] [3] [4] [5] (1 st Treatment Visit)	Visit 4 [2] [3] [5] (2 nd Treatment Visit)	Visit 5 ADA Assessment Visit [6]	Visit 6 Follow-Up [7]
Standardized lunch [18]			X	X		
In-clinic exercise [19]			X	X		
Questionnaires (pre & post BP)			X	X		
ADA			X [20]		X	X
Adverse event review			X	X	X	X

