
3.2 Trial Endpoints

3.2.1 Primary Endpoint

The primary endpoint is the safety and tolerability of ZP4207 in the BP using either the iLet or the iPhone platform as assessed by

- Number and type of adverse events (AEs)
- Clinical laboratory measurements
- Vital signs
- 12-lead electrocardiograms (ECGs)
- Local tolerability and infusion site reactions as measured with the Draize scale
- Immunogenicity as measured by anti-drug antibodies (ADA)
- Pain as measured on a 10 cm visual analog scale (VAS)
- Nausea as measured on a 10 cm VAS

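### The laboratory abnormality counts in SAP section 4.6.2 do not link visit-end to visit-start results, so the number of patients who became abnormal during a visit cannot in general be read from them

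*SAP*

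**What the plan says.** Laboratory data are one component of the primary safety endpoint: section 3.2.1 lists "Clinical laboratory measurements". In Table 1 (section 3.1) the row "Safety lab sampling including chemistry and hematology" is marked at Visits 3 and 4 with footnote 10, which reads "10. At visit start and visit end". Each treatment visit therefore yields a pair of results per patient.

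Section 4.6.2 plans four outputs:

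- Descriptive statistics by treatment sequence, at visit start and visit end within each period.
- A change summary: "Change from the start of the visit will also be summarized by treatment".
- A categorical summary: "Frequency counts and percentages of patients with normal and abnormal results, for parameters of interest, will also be presented by treatment sequence".
- Listings: "Listings of patients with abnormal results will be provided".

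The visit-start result serves as a reference only in the second output, which is continuous. Neither this section nor any other part of the SAP mentions a shift table, defines a newly abnormal result, or restricts the counts to patients who started the visit normal. Section 4.6 says that the safety results will be compared qualitatively between the two treatments.

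**The concern.** The purpose of counting abnormal laboratory results in a safety trial is to see how many patients moved out of range while on each drug. That is a statement about pairs: normal before, abnormal after. A count of patients in and out of range is a marginal summary. It can be identical at start and end when nobody changed, and equally when several patients became abnormal while as many returned to normal. The reader who wants the number of new abnormalities under ZP4207 and under Lilly glucagon would have to rebuild it from the listings, although the paired data are collected and one standard table would show it.

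**Working it through.** The SAP gives no abnormality rates, so there is no figure of its own to reproduce. The check is what the planned counts can and cannot determine.

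**Inputs.** Section 3.1 expects up to 10 completers in each part and randomizes in blocks of 2. I therefore use n = 10 for a part and n = 5 for one sequence within a part (assuming 10 completers, equally split). Let a be the number abnormal at visit start and b the number abnormal at visit end for one parameter. The values of a and b below are illustrative.

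**Step 1: bounds.** Let x be the number normal at start and abnormal at end. Then x cannot exceed b, nor the n − a patients who started normal. The other b − x patients abnormal at end must be among the a who started abnormal, so x is at least b − a. Hence

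max(0, b − a) ≤ x ≤ min(b, n − a).

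**Step 2: numbers.**

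| n | a | b | Lowest x | Highest x |
|---|---|---|---|---|
| 10 | 4 | 4 | max(0, 0) = 0 | min(4, 6) = 4 |
| 10 | 3 | 3 | 0 | min(3, 7) = 3 |
| 10 | 2 | 3 | 1 | min(3, 8) = 3 |
| 5 | 2 | 2 | 0 | min(2, 3) = 2 |

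In the first row, the share of initially normal patients who became abnormal could be anything from 0/6 to 4/6 (0% to 67%).

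**Step 3: when the counts suffice.** The width of the interval is min(b, n − a) − max(0, b − a) = min(a, b, n − a, n − b). It is zero only if a or b equals 0 or n. Enumeration agrees. For n = 5 there are 36 possible pairs (a, b); none of the 16 with both counts strictly between 0 and n fixes x, and the other 20 do. For n = 10 there are 121 pairs; none of the 81 interior ones fixes x, and the other 40 do.

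**Step 4: how often the start count might be zero.** If a fraction p of patients is out of range at start on a given parameter, independently (both assumed), the chance that a = 0 is (1 − p)^n.

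| p | n = 5 | n = 10 |
|---|---|---|
| 5% | 0.95^5 = 0.77 | 0.95^10 = 0.60 |
| 10% | 0.90^5 = 0.59 | 0.90^10 = 0.35 |
| 20% | 0.80^5 = 0.33 | 0.80^10 = 0.11 |

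For a rarely abnormal parameter, separate start and end counts would often be enough. For a parameter that is commonly abnormal before dosing, they usually would not be, unless the end count is itself 0 or n.

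**Step 5: the other outputs.** The change summary describes the size of change, not whether a reference limit was crossed. The listings hold the information patient by patient but do not tabulate it.

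**The case against.** The strongest reply is that the information is not lost, and most of that reply stands.

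- A reader might infer that the change summary shows means only. Section 4.1 defines continuous summaries as including median, SD, minimum and maximum, so with about 10 patients the most extreme change under each drug will be visible.
- A reader might infer that abnormalities present before dosing are mixed with later ones. The frequency sentence does not repeat the time points, but the section's first sentence fixes start and end of visit within each period, and the natural reading carries these over. Abnormalities at visit start would then be visible in aggregate.
- Section 4.1 commits to listing all data by patient, so start and end values can be compared by hand in a trial of this size.
- Section 4.6.1 names an abnormal laboratory finding as an example of an adverse event, and events are listed with the treatment period at onset. A new abnormality can therefore be reported by that route, although the SAP does not say that every out-of-range result becomes an adverse event.
- Section 6.2 leaves mock-up tables to separate specifications, which could include a shift layout. The SAP does not commit to one.

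These points lower the importance. They do not enable the planned count table to show who crossed a limit, and no other planned summary does so by drug.

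**Conclusion.** The point holds, at low severity. As written, the categorical laboratory summary does not determine the number of patients who became abnormal during a treatment visit unless a start or end count is 0 or n. The uncertainty can be as wide as 0 to 4 new cases among 10 patients in the example. This algebra needs no assumption about abnormality rates; only the frequency with which the problem would arise depends on them, and the SAP gives none.

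It would be tempting to go further and say that drug-related abnormalities are masked, or that the table would mostly reflect the background state of the patients. The documents do not support that: the parameters of interest are not named, all data are listed, and the comparison is descriptive and qualitative. No estimate or test changes.

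I take visit start to mean before that visit's dosing. At Visit 4 it is not before any trial drug, because the patient was dosed at Visit 3.

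**What to change.** In section 4.6.2, replace the frequency-count sentence with a commitment along these lines:

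> For each parameter of interest, a shift table (low, normal, high at visit start against low, normal, high at visit end) will be given by treatment within each part. It will include the number and percentage of patients normal at start and abnormal at end. Patients abnormal at start will be shown separately. At each visit, start means before that visit's dosing.

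The percentage should state its denominator, for which patients normal at start with both results available is the obvious choice. Presenting the table by treatment also matches the comparison between treatments that section 4.6 announces.

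The cost is a change of SAP wording and one standard table in place of another. No new data, test or change in sample size is needed.
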